## **8. ADVERSE EVENT REPORTING**

### **8.1. Adverse Events**

All observed or volunteered adverse events regardless of treatment group or suspected causal relationship to the investigational product(s) will be reported as described in the following sections.

For all adverse events, the investigator must pursue and obtain information adequate both to determine the outcome of the adverse event and to assess whether it meets the criteria for classification as a serious adverse event requiring immediate notification to Pfizer or its designated representative. For all adverse events, sufficient information should be obtained by the investigator to determine the causality of the adverse event. The investigator is required to assess causality. For adverse events with a causal relationship to the investigational product, follow-up by the investigator is required until the event or its sequel resolve or stabilize at a level acceptable to the investigator.

### **8.2. Reporting Period**

For serious adverse events, the reporting period to Pfizer or its designated representative begins from the time that the subject provides informed consent, which is obtained prior to the subject's participation in the study, ie, prior to undergoing any study-related procedure and/or receiving investigational product, through and including 28 calendar days after the last administration of the investigational product. Any serious adverse event occurring any time after the reporting period must be promptly reported if a causal relationship to investigational product is suspected.

- Adverse events (serious and non-serious) should be recorded on the CRF from the time the subject has taken at least one dose of study treatment through last subject visit.

### **8.3. Definition of an Adverse Event**

An adverse event is any untoward medical occurrence in a clinical investigation subject administered a product or medical device; the event need not necessarily have a causal relationship with the treatment or usage. Examples of adverse events include but are not limited to:

- Abnormal test findings;
- Clinically significant symptoms and signs;
- Changes in physical examination findings;
- Hypersensitivity;
- Progression/worsening of underlying disease.

Additionally, they may include the signs or symptoms resulting from:

- Drug overdose;

- Drug withdrawal;
- Drug abuse;
- Drug misuse;
- Drug interactions;
- Drug dependency;
- Exposure during pregnancy;
- Exposure during breast feeding.

#### **8.4. Abnormal Test Findings**

The criteria for determining whether an abnormal objective test finding should be reported as an adverse event are as follows:

- Test result is associated with accompanying symptoms, and/or
- Test result requires additional diagnostic testing or medical/surgical intervention, and/or
- Test result leads to a change in study dosing or discontinuation from the study, significant additional concomitant drug treatment, or other therapy, and/or
- Test result is considered to be an adverse event by the investigator or sponsor.

Merely repeating an abnormal test, in the absence of any of the above conditions, does not constitute an adverse event. Any abnormal test result that is determined to be an error does not require reporting as an adverse event.

#### **8.5. Serious Adverse Events**

A serious adverse event is any untoward medical occurrence at any dose that:

- Results in death;
- Is life-threatening (immediate risk of death);
- Requires inpatient hospitalization or prolongation of existing hospitalization;
- Results in persistent or significant disability/incapacity;
- Results in congenital anomaly/birth defect.

Medical and scientific judgment is exercised in determining whether an event is an important medical event. An important medical event may not be immediately life-threatening and/or result in death or hospitalization. However, if it is determined that the event may jeopardize the subject or may require intervention to prevent one of the other adverse event outcomes, the important medical event should be reported as serious.

Examples of such events are intensive treatment in an emergency room or at home for allergic bronchospasm; blood dyscrasias or convulsions that do not result in hospitalization; or development of drug dependency or drug abuse.

### **8.5.1. Potential Cases of Drug-Induced Liver Injury**

Abnormal values in aspartate transaminase (AST) and/or alanine transaminase (ALT) concurrent with abnormal elevations in total bilirubin that meet the criteria outlined below in the absence of other causes of liver injury are considered potential cases of drug-induced liver injury (potential Hy's Law cases) and should always be considered important medical events.

The threshold of laboratory abnormalities for a potential case of drug-induced liver injury depends on the subject's individual baseline values and underlying conditions. Subjects who present with the following laboratory abnormalities should be evaluated further to definitively determine the etiology of the abnormal laboratory values:

- A. *Subjects with AST or ALT baseline values within the normal range* who subsequently present with AST or ALT  $\geq 3$  times the upper limit of normal concurrent with a total bilirubin  $\geq 2$  times the upper limit of normal with no evidence of hemolysis and an alkaline phosphatase  $\leq 2$  times the upper limit of normal or not available.
- B. *Subjects with pre-existing AST or ALT baseline values above the normal range* who subsequently present with AST or ALT  $\geq 2$  times the baseline values and  $\geq 3$  times the upper limit of normal, or  $\geq 8$  times the upper limit of normal (whichever is smaller) concurrent with a total bilirubin of  $\geq 2$  times the upper limit of normal and increased by one upper limit of normal over baseline or  $>3$  times the upper limit of normal (whichever is smaller) with no evidence of hemolysis and an alkaline phosphatase  $\leq 2$  times the upper limit of normal or not available.

The subject should return to the investigational site and be evaluated as soon as possible, preferably within 48 hours from awareness of the abnormal results. This evaluation should include laboratory tests, detailed history and physical assessment and for oncology studies, the possibility of hepatic neoplasia (primary or secondary) should be considered). In addition to repeating AST and ALT, laboratory tests should include albumin, creatine kinase, total bilirubin, direct and indirect bilirubin, gamma-glutamyl transferase (GGT), international normalized ratio (INR) and alkaline phosphatase. A detailed history, including relevant information, such as review of ethanol, recreational drug and supplement consumption, family history, sexual history, travel history, history of contact with a jaundiced subject, surgery, blood transfusion, history of liver or allergic disease, and work exposure, should be collected. Further testing for acute hepatitis A, B, or C infection and liver imaging (eg, biliary tract) may be warranted. All cases confirmed on repeat testing as meeting criteria A or B, with no other cause for LFT abnormalities identified at the time should be considered potential Hy's Law cases irrespective of availability of all the results of the investigations performed to determine etiology of the abnormal LFTs. Such potential Hy's Law cases should be reported as serious adverse events.

### **8.6. Hospitalization**

Adverse events reported from studies associated with hospitalization or prolongations of hospitalization are considered serious. Any initial admission (even if less than 24 hours) to a healthcare facility meets these criteria. Admission also includes transfer within the hospital to

an acute/intensive care unit (eg, from the psychiatric wing to a medical floor, medical floor to a coronary care unit, neurological floor to a tuberculosis unit).

Hospitalization does not include the following:

- Rehabilitation facilities;
- Hospice facilities;
- Respite care (eg, caregiver relief);
- Skilled nursing facilities;
- Nursing homes;
- Routine emergency room admissions;
- Same day surgeries (as outpatient/same day/ambulatory procedures).

Hospitalization or prolongation of hospitalization in the absence of a precipitating, clinical adverse event is not in itself a serious adverse event. Examples include:

- Admission for treatment of a preexisting condition not associated with the development of a new adverse event or with a worsening of the preexisting condition (eg, for work-up of persistent pre-treatment lab abnormality);
- Social admission (eg, subject has no place to sleep);
- Administrative admission (eg, for yearly physical exam);
- Protocol-specified admission during a study (eg, for a procedure required by the study protocol);
- Optional admission not associated with a precipitating clinical adverse event (eg, for elective cosmetic surgery);
- Hospitalization for observation without a medical AE;
- Pre-planned treatments or surgical procedures should be noted in the baseline documentation for the entire protocol and/or for the individual subject.

Diagnostic and therapeutic non-invasive and invasive procedures, such as surgery, should not be reported as adverse events. However, the medical condition for which the procedure was performed should be reported if it meets the definition of an adverse event. For example, an acute appendicitis that begins during the adverse event reporting period should be reported as the adverse event, and the resulting appendectomy should be recorded as treatment of the adverse event.

## **8.7. Severity Assessment**

If required on the adverse event case report forms, the investigator will use the adjectives MILD, MODERATE, or SEVERE to describe the maximum intensity of the adverse event. For purposes of consistency, these intensity grades are defined as follows:

MILD	Does not interfere with subject's usual function.
MODERATE	Interferes to some extent with subject's usual function.
SEVERE	Interferes significantly with subject's usual function.

Note the distinction between the severity and the seriousness of an adverse event. A severe event is not necessarily a serious event. For example, a headache may be severe (interferes significantly with subject's usual function) but would not be classified as serious unless it met one of the criteria for serious adverse events, listed above.

## **8.8. Causality Assessment**

The investigator's assessment of causality must be provided for all adverse events (serious and non-serious); the investigator must record the causal relationship in the CRF, as appropriate, and report such an assessment in accordance with the serious adverse reporting requirements if applicable. An investigator's causality assessment is the determination of whether there exists a reasonable possibility that the investigational product caused or contributed to an adverse event. If the investigator does not know whether or not investigational product caused the event, then the event will be handled as "related to investigational product" for reporting purposes, as defined by the Sponsor (see Section on Reporting Requirements). If the investigator's causality assessment is "unknown but not related to investigational product", this should be clearly documented on study records.

In addition, if the investigator determines a serious adverse event is associated with study procedures, the investigator must record this causal relationship in the source documents and CRF, as appropriate, and report such an assessment in accordance with the serious adverse event reporting requirements, if applicable.

## **8.9. Withdrawal Due to Adverse Events**

Withdrawal due to adverse event should be distinguished from withdrawal due to insufficient response, according to the definition of adverse event noted earlier, and recorded on the appropriate adverse event CRF page.

When a subject withdraws due to a serious adverse event, the serious adverse event must be reported in accordance with the reporting requirements defined below.

## **8.10. Eliciting Adverse Event Information**

The investigator is to report all directly observed adverse events and all adverse events spontaneously reported by the study subject. In addition, each study subject will be questioned about adverse events.

## **8.11. Reporting Requirements**

Each adverse event is to be assessed to determine if it meets the criteria for serious adverse events. If a serious adverse event occurs, expedited reporting will follow local and international regulations, as appropriate.

### **8.11.1. Serious Adverse Event Reporting Requirements**

If a serious adverse event occurs, Pfizer is to be notified within 24 hours of awareness of the event by the investigator. In particular, if the serious adverse event is fatal or life-threatening, notification to Pfizer must be made immediately, irrespective of the extent of available adverse event information. This timeframe also applies to additional new information (follow-up) on previously forwarded serious adverse event reports as well as to the initial and follow-up reporting of exposure during pregnancy and exposure during breast feeding cases.

In the rare event that the investigator does not become aware of the occurrence of a serious adverse event immediately (eg, if an outpatient study subject initially seeks treatment elsewhere), the investigator is to report the event within 24 hours after learning of it and document the time of his/her first awareness of the adverse event.

For all serious adverse events, the investigator is obligated to pursue and provide information to Pfizer in accordance with the timeframes for reporting specified above. In addition, an investigator may be requested by Pfizer to obtain specific additional follow-up information in an expedited fashion. This information collected for serious adverse events is more detailed than that captured on the adverse event case report form. In general, this will include a description of the adverse event in sufficient detail to allow for a complete medical assessment of the case and independent determination of possible causality. Information on other possible causes of the event, such as concomitant medications and illnesses must be provided. In the case of a subject death, a summary of available autopsy findings must be submitted as soon as possible to Pfizer or its designated representative.

### **8.11.2. Non-Serious Adverse Event Reporting Requirements**

All adverse events will be reported on the adverse event page(s) of the CRF. It should be noted that the form for collection of serious adverse event information is not the same as the adverse event CRF. Where the same data are collected, the forms must be completed in a consistent manner. For example, the same adverse event term should be used on both forms. Adverse events should be reported using concise medical terminology on the CRFs as well as on the form for collection of serious adverse event information.

### **8.11.3. Sponsor Reporting Requirements to Regulatory Authorities**

Adverse events reporting, including suspected serious unexpected adverse reactions, will be carried out in accordance with applicable local regulations.

## **9. DATA ANALYSIS/STATISTICAL METHODS**

### **9.1. Sample Size Determination**

The study is designed to provide 90% power to detect a difference of at least 1.1 (a clinically meaningful difference) in the pain severity score from baseline between pregabalin-treated

subjects and placebo at an alpha level of 0.05, a tolerance for type II error set at beta 0.10, and a common SD of 2. This requires 20 patients in each group for a total of 40 patients.

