### **9.1.1. Analysis of Primary Endpoint**

- To evaluate efficacy, we will compare the endpoint mean pain score for the Lyrica group compared to the placebo group using an analysis of covariance (ANCOVA) model with treatment and center as main effects and the baseline PI score as a covariate.
- A BOCF and a modified or hybrid approach (mBOCF) will be used to account for missing data at last treatment Week. As a sensitivity we will look at the LOCF, MMRM and the missing imputation (suggested the National Academy of Sciences report).

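### Twenty patients per group give about 40% power, not 90%, for a 1.1-point difference with SD 2; 90% needs about 71 per group

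*Combined protocol and SAP*

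**What the plan says.** Section 9.1 is a single self-contained statement. It opens: "The study is designed to provide 90% power to detect a difference of at least 1.1 (a clinically meaningful difference". It sets the significance level ("at an alpha level of 0.05"), the type II error ("a tolerance for type II error set at beta 0.10") and the variability ("a common SD of 2"), and ends: "This requires 20 patients in each group for a total of 40 patients".

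It does not say whether alpha is one- or two-sided, makes no allowance for dropout, and gives no correlation between baseline and endpoint pain. Sections 3 and 5.1 set 1:1 randomisation to two parallel arms. Section 9.1.1 plans the primary comparison "using an analysis of covariance (ANCOVA) model with treatment and center as main effects and the baseline PI score as a covariate".

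**The concern.** The target difference is 1.1/2 = 0.55 of an SD. Detecting an effect of that size with 90% power normally takes roughly 70 patients per arm, so 20 per arm is too few by a factor of about 3.5. Rounding cannot explain a gap that large.

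The number is the only quantitative justification for the size of the trial. Section 1.2 says that no study has directly examined pregabalin in idiopathic, biopsy-proven small fiber neuropathy, so a non-significant result could carry a lot of weight. Read as coming from a 90%-power trial, it could be taken as evidence against the drug when the trial had little chance of detecting the effect it was set up to find.

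**Working it through.** **Inputs.** From Section 9.1: difference 1.1, SD 2 in both arms, alpha 0.05, power 0.90, stated size 20 per group. From Sections 3 and 5.1: 1:1 allocation. Sidedness is not stated; two-sided is assumed first, then one-sided. No dropout is applied.

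**Trying to reproduce 20 per group.** Normal approximation, two-sided:

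- n per group = 2 × (1.960 + 1.282)² × (2/1.1)² = 69.5, so 70.
- With the exact noncentral t: 70 per group gives 89.8% power and 71 gives 90.2%, so 71 per group (142 in total).

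The stated 20 is not reproduced.

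**Power with 20 per group.**

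- Standard error of the difference = 2 × √(2/20) = 0.632.
- Normal approximation: Φ(1.1/0.632 − 1.960) = 41.3%.
- Exact t-test, 38 degrees of freedom: 39.6%.

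**What 20 per group can show at SD 2 (two-sided, unadjusted).**

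- Difference detectable with 90% power: 1.052 × 2 = 2.1 points; with 80% power: 1.8 points.
- 95% confidence interval half-width: 2.024 × 0.632 = 1.28 points, which is wider than the 1.1-point target.
- An observed difference of exactly 1.1 gives t = 1.1/0.632 = 1.74, p = 0.09.

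**Other readings of the same inputs** (exact t):

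| Reading | n for 90% power | Power at 20 per group |
|---|---|---|
| Two-sided, two groups | 71 per group | 39.6% |
| One-sided 0.05, two groups | 58 per group | 52.5% |
| 2 taken as a variance, two-sided | 36 per group | 67% |
| Paired or one-sample formula, two-sided | 37 in total | not this design |

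Reading the total of 40 as 40 per group gives 68% two-sided. The one-sample result of 37 does fall just below 40, so a one-sample formula might have been used by mistake. That is conjecture, and the design compares two parallel arms.

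**What would make 20 per group correct.** For 90% two-sided power the SD must be 1.1/1.052 = 1.05 (1.17 if one-sided).

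**ANCOVA.** If 2 is the unadjusted SD and r is the baseline-outcome correlation, the residual SD is 2 × √(1 − r²). Setting this to 1.05 gives r = 0.85 (0.81 if one-sided). The documents give no r, so the values below are assumptions:

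| Assumed r | Residual SD | Two-sided power at 20 per group | n per group for 90% (normal approximation) |
|---|---|---|---|
| 0.5 | 1.73 | 50% | 53 |
| 0.6 | 1.60 | 56% | 45 |
| 0.7 | 1.43 | 66% | 36 |

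**The case against.** The best counter-argument is that 40% describes an analysis that is not planned. The primary analysis is an ANCOVA on baseline pain, which is more efficient than a t-test if 2 is the raw SD. On the assumed range of r from 0.5 to 0.7, the chance of missing a 1.1-point effect falls from about 60% to between 50% and 34%, and the 1.28 half-width and p = 0.09 would shrink as well. The enriched design is also said in Section 1.2 to increase power.

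Part of this stands. The figures of 40% and 71 are the unadjusted, two-sided case, or the case in which 2 is already the residual SD, and they must be labelled so. It is also unclear which SD is meant: Section 9.1 speaks of a score relative to baseline, while Sections 2.2 and 9.1.1 use the endpoint mean. If 2 is the SD of a change score, it may already include some of the gain from adjustment.

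The argument does not rescue the stated size. Reaching 90% needs a correlation above 0.8 even with one-sided testing, and the protocol neither states nor supports one. The remark on enrichment carries no number and cannot override an SD stated as 2. Any dropout allowance would push the required number up.

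**Conclusion.** The concern holds. As written, Section 9.1 is arithmetically wrong: its own inputs give 39.6% power at 20 per group and require 71 per group for 90%, assuming a two-sided, unadjusted comparison without dropout. The one-sided equivalents are 52.5% and 58. Assumed baseline correlations of 0.5 to 0.7 raise two-sided power to between 50% and 66%, still well short of 90%. No reading of the stated inputs that was tried yields 20 per group. It is a must-fix point, held with high confidence. The one thing the documents leave open is whether the SD of 2 is itself a misprint or a different kind of SD from the one the calculation used; in either case the current text needs correcting.

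**What to change.** Rewrite Section 9.1 so that inputs, power and sample size agree.

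- If 40 patients and SD 2 stay, state about 40% power for 1.1 points, or 90% power for about 2.1 points, labelled as two-sided and unadjusted. Any higher power claimed for ANCOVA should come with the assumed correlation and its source.
- If 2 was not the intended SD, or a residual SD after adjustment was meant, state that SD, whether it refers to the endpoint or to change from baseline, and its source. About 1.05 is needed for 20 per group at two-sided 0.05.
- State whether alpha is two-sided.
- Record that about 71 per group, before dropout, is the size that delivers the claimed power under the stated inputs without adjustment.

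Describing the trial as preliminary, with the confidence interval as its main result, would suit 40 patients but is optional.

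The cost is a wording change and a less favourable power statement. Correcting the claim needs no extra patients and no change to treatment or analysis; enlarging the trial would be a separate decision.

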### **9.1.1. Analysis of Primary Endpoint**

- To evaluate efficacy, we will compare the endpoint mean pain score for the Lyrica group compared to the placebo group using an analysis of covariance (ANCOVA) model with treatment and center as main effects and the baseline PI score as a covariate.
- A BOCF and a modified or hybrid approach (mBOCF) will be used to account for missing data at last treatment Week. As a sensitivity we will look at the LOCF, MMRM and the missing imputation (suggested the National Academy of Sciences report).

### **9.1.2. Analysis of Secondary Endpoints**

Secondary analyses included examination of the PGIC and sleep interference rate will be compared between treatment groups using a Cochran-Mantel-Haenszel test.

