#### **4.3. Randomization Criteria**

A list of allowed and disallowed concomitant pain medication is provided in sections 5.3.7 and 5.3.8. If patients is on any of the disallowed pain medications, this medication will be discontinued during the washout phase with an appropriate taper schedule based on the clinician judgment. Subjects must meet the following criteria after the washout period to be randomized for single-blind pregabalin treatment phase:

1. Subjects must have worsening in neuropathic pain from baseline to the end of washout phase.
2. Subjects must have an average pain score  $\geq 8$  in the final week of washout phase.

Subjects must meet the following criteria after the single-blind pregabalin treatment phase to be randomized for withdrawal phase:

1. Subjects must have response to treatment defined as at least one point decrease in pain intensity score at the end of the single-blind pregabalin treatment phase.

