### **7.3.4. Patient Global Impression of Change (PGIC)**

The PGIC is a subject rated global measure that provides a clinically relevant and easy to interpret account of a patient’s perception of the clinical importance of their improvement or worsening during their involvement in a clinical study. Subjects rate their overall improvement on a 7-point scale where scores range from 1 (very much improved) to 7 (very much worse).

The PGIC is recommended by the Initiative on Methods, Measurement, and Pain Assessment in Clinical Trials (IMMPACT) as a measure of “participant rating of global improvement and satisfaction with treatment.” It is one of six core outcomes measures recommended for use in clinical trials of chronic pain treatment efficacy and effectiveness. The PGIC will be completed by the subject at Visits 5 and 6. Completion instructions for subjects will indicate that global improvement refers to the condition under study.

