## APPENDIX 1. SCHEDULE OF ACTIVITIES

The Schedule of Activities table provides an overview of the protocol visits and procedures. Refer to Study Procedures and Assessments for detailed information on each procedure and assessment required for compliance with the protocol.

Study Phase:	Baseline (V1 to V2)	Single-Blind Treatment Phase (8 weeks)						Randomized Withdrawal Phase (4 weeks)
		V1 a,c	V2 a,c	V3	V4	V5	V6	
Clinic Visit No.:	V1 a,c	V1 a,c	V2 a,c	V3	V4	V5	V6	V7
Visit:	Screening	Enrollment	Wk 1	Wk2	Wk 4	Wk 8		Wk 12
Study Day:	-30 to -14	0	7	14	28	56		84
Visit Type:	Clinic	Clinic	Phone	Phone	Phone	Clinic		Clinic
Visit Window:	N/A	7 - 21 days	±2 days	±2 days	±2 days	±3 days		±3 days
Observation/Procedure								
Informed consent b	X							
Inclusion/Exclusion	X	X						
Medical History	X							
Physical exam/Neurological exam	X							X
Vital Signs e	X	X						X
Clinical labs	X							
Retained blood sample for proteomics, etc.	X							
IENF biopsy	X							
PainDETECT	X							
PHQ-8	X							
Suicidality Assessment (C-SSRS)	X	X					X	X
Adverse Events	X	X	X	X	X	X		X
Concomitant/Rescue medications f	X	X	X	X	X	X		X
Study medication dispensing		X				X		X
NPSI		X				X		X

Study Phase:	Baseline (V1 to V2)	Single-Blind Treatment Phase (8 weeks)					Randomized Withdrawal Phase (4 weeks)
SFN-SIQ		X				X	X
Numeric Rating Scale for Pain (NRS-Pain - 1 week recall)	X						
IVRS Daily Diary, (Pain NRS and SIRS)	X	X	X	X	X	X	X
Brief Pain Inventory - short form (BPI- sf)	X	X				X	X
EuroQOL 5-Dimensions (EQ-5D)		X				X	X
Patient Global Impression of Change (PGIC)						X	X

- a Visit 1 may occur between 30 days and 14 days prior to Visit 2, based on the amount of time required for screening procedures such as punch biopsy or washout period for previous pain medications. The screening visit may also be split into two visits. A 14-day minimum baseline between Visit 1 and Visit 2 is required to establish baseline pain level. The maximum 30-day screening period does not include prior completion of the informed consent.
- b Informed consent must be completed prior to performing any other study procedures, including any medication changes made to participate in the study. Any such medication changes must be considered for medical appropriateness to protect patient well-being.
- c V2 is the Single-blind Baseline visit (enrollment).

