- d V6 is the final visit of the single-blind phase and also the randomization visit for subjects who are eligible to continue in the withdrawal phase.
- e Includes weight, blood pressure, and pulse at all clinic visits, and height at Visit 1 only.
- f Rescue medications may NOT be taken within the 2 hours prior to daily diary completion

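### The planned PGIC test names no visit and makes no use of the Visit 6 rating, which costs power but does not bias the result; the PGIC visits conflict and must be settled first

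*Combined protocol and SAP*

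**What the plan says.** **Analysis.** Section 9.1.2 states: "Secondary analyses included examination of the PGIC and sleep interference rate will be compared between treatment groups using a Cochran-Mantel-Haenszel test." It gives no visit, category scores, strata or covariate. Section 9.1.1, in contrast, adjusts the primary endpoint for baseline pain and centre.

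**Instrument.** Section 7.3.4 describes a 7-point rating, from 1 (very much improved) to 7 (very much worse), of the patient's view of "the clinical importance of their improvement or worsening during their involvement in a clinical study". On completion it says: "Completion instructions for subjects will indicate that global improvement refers to the condition under study." That fixes the condition rated but not the start of the comparison. No section resets the reference at randomisation.

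**Visits.** Section 7.3.4: "The PGIC will be completed by the subject at Visits 5 and 6." The marks in the Appendix 1 PGIC row read as Visits 6 and 7. The assessment lists for Visit 6 (Section 6.2.5) and Visit 7 (Section 6.2.6) do not include the PGIC. A note to Appendix 1 says: "V6 is the final visit of the single-blind phase and also the randomization visit for subjects who are eligible to continue in the withdrawal phase."

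**Design.** Washout is followed by 8 weeks of single-blind pregabalin and a 4-week randomised withdrawal phase (Section 3). Section 4.3 randomises patients with "at least one point decrease in pain intensity score at the end of the single-blind pregabalin treatment phase". Section 6.2.5.2 keeps patients unaware that randomisation takes place. Global assessment is the first secondary objective (Section 2.1).

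**The concern.** A patient rating change over the whole study at Visit 7 is rating washout, 8 weeks on pregabalin and 4 randomised weeks together. Only the last part differs by arm. Because patients do not know that randomisation has occurred, they have no reason to restart the comparison themselves. Differences in how far patients moved before Visit 6 then enter the Visit 7 score as noise.

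A Visit 6 PGIC would be on the same scale, would precede randomised treatment, and would probably predict the Visit 7 score. Section 9.1.2 does not use it. At stake is the precision of the test for the first secondary objective in a trial of 40 patients. If Section 7.3.4 governs the visits, there would be no rating after randomised treatment to compare at all.

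**Working it through.** **1. Is there a rating to compare?**

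| Source | PGIC visits | Any after randomised treatment? |
|---|---|---|
| Section 7.3.4 | 5 (Day 28), 6 (Day 56) | No |
| Appendix 1, as the row reads | 6, 7 | Yes, Visit 7 |
| Sections 6.2.5 and 6.2.6 | not listed | No |

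Visit 6 is the only visit that Section 7.3.4 and Appendix 1 share. The steps below take the Appendix 1 reading.

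**2. Bias.** Write the Visit 7 state as A + C, where A is the state at Visit 6 and C the change afterwards. A precedes randomised treatment, so its expectation is the same in both arms. The expected arm difference at Visit 7 is therefore the difference in C alone. What A adds is variance. If the two ratings correlate at r, linear adjustment multiplies the residual variance by 1 − r².

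**3. Closed-form size.** The plan claims no power for the PGIC, so there is no figure to reproduce. Inputs are n = 20 per arm and alpha 0.05 (Section 9.1). Two-sided testing, complete data and a standardised difference d = 0.8 are assumed.

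Power = Φ( d·√(n/2) / √(1 − r²) − 1.96 )

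- Unadjusted: 0.8 × √10 = 2.530; 2.530 − 1.960 = 0.570; power 71.6%.
- r = 0.3: 1 − r² = 0.91; power 75.6%, a gain of 4 points.
- r = 0.5: 1 − r² = 0.75; power 83.2%, a gain of 12 points.
- r = 0.7: 1 − r² = 0.51; power 94.3%, a gain of 23 points.

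**4. Simulation on the 7-category scale.** All PGIC inputs are assumed. The latent Visit 6 score has mean 2.3 and SD 0.9. Visit 7 adds a drift of 0.3, normal change with the SD shown and, on placebo, the worsening shown. Scores are rounded to 1–7. There are 20 per arm and 6,000 trials per row. The stratified CMH test uses Visit 6 scores 1, 2, 3 and 4 or more.

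| Change SD (null correlation) | Placebo worsening, categories | CMH, no Visit 6 | CMH, 4 strata | ANCOVA on Visit 6 | ANCOVA gain, points |
|---|---|---|---|---|---|
| 0.7 (0.72) | 0 | 4.9% | 5.0% | 5.4% | – |
| | 0.5 | 25.5% | 43.0% | 46.1% | 20.6 |
| | 0.8 | 53.5% | 81.5% | 84.1% | 30.6 |
| | 1.0 | 73.4% | 94.1% | 95.6% | 22.2 |
| 1.0 (0.60) | 0 | 5.1% | 5.1% | 5.3% | – |
| | 0.5 | 19.7% | 26.3% | 28.4% | 8.7 |
| | 0.8 | 42.0% | 57.3% | 60.5% | 18.5 |
| | 1.0 | 59.9% | 75.9% | 79.3% | 19.4 |
| 1.4 (0.49) | 0 | 5.2% | 5.1% | 4.8% | – |
| | 0.5 | 14.1% | 16.5% | 17.3% | 3.2 |
| | 0.8 | 30.5% | 34.6% | 36.6% | 6.1 |
| | 1.0 | 42.7% | 50.4% | 53.5% | 10.8 |

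**5. A second set of assumptions.** Single-blind improvement has mean 2.5 and SD 1.5, kept only if at least 1 point, with reporting noise SD 0.7. There are 20 per arm and 4,000 trials per setting. The CMH test is stratified coarsely (Visit 6 score 1–2 against 3 or more).

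| Placebo loss, points | Change SD | CMH, no Visit 6 | CMH, 2 strata | ANCOVA |
|---|---|---|---|---|
| 1.1 | 1.0 | 47.5% | 53.9% | 58.6% |
| 1.1 | 1.5 | 33.9% | 37.3% | 40.3% |
| 1.5 | 1.0 | 74.0% | 79.6% | 84.6% |
| 1.5 | 1.5 | 58.2% | 62.2% | 65.1% |

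ANCOVA gains 11.1, 6.4, 10.6 and 6.9 points; two-stratum CMH gains 6.4, 3.4, 5.6 and 4.0. With no loss, rejection was 3.9% to 5.4%. This set omits washout.

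**6. A third set**, in which the gain persisted when washout worsening was included, gave about 2 to 19 points for ANCOVA and about −1 to +10 for stratified CMH, with type I error near 5%.

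**The case against.** Several stronger readings are tempting, and the documents do not support them.

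- *The Visit 7 comparison is biased or answers the wrong question.* A reader might infer this because the rating spans uncontrolled weeks. Step 2 shows otherwise: the arm contrast reflects what followed randomisation, and the null rejection rates are near 5%.
- *Every randomised patient has improved since entry.* This does not follow. First-visit pain must be above 3 and below 8 (Section 4.1), and the washout average must reach at least 8 (Section 4.3). If the one-point response is counted from Visit 2, which Appendix 1 calls the single-blind baseline, a patient at 5, then 8, then 7 qualifies and is 7 − 5 = 2 points worse than at entry.
- *The PGIC question certainly covers the whole study.* The wording in Section 7.3.4 describes the instrument in general terms, and the item text is not in the documents. That reference period is the natural reading, not a stated one.
- *The plan rules out using Visit 6.* It is silent. CMH is a stratified method and could take Visit 6 as a stratum. Silence does, however, leave that choice open until data are seen.
- *Visit 6 would separate the two phases.* Adjustment removes carried-over variation; two ordinal ratings do not subtract exactly.
- *A null result would follow from most patients still rating themselves improved.* CMH compares arms, not the share improved, and how readers would take that share is speculation.

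The objection that stands most firmly is that the Visit 7 rating rests on Appendix 1 alone, so the remedy cannot be run until the schedule is reconciled. It is also fair that every power figure depends on assumed inputs.

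**Conclusion.** The point holds as one of efficiency and specification. If the PGIC is collected at Visits 6 and 7, leaving out Visit 6 costs roughly 2 to 19 points of power against a linear model. That range fits the rows above with change SD 1.0 or 1.4 (3 to 19 points) and the second set (6 to 11). Gains of 21 to 31 points appear only where the ratings correlate at about 0.7. A two-stratum CMH test gains less and may gain nothing.

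These sizes assume 20 complete patients per arm and PGIC variances that the documents do not give; only their direction is secure. The conflict over visits needs no assumption, and it comes first because one of the stated schedules leaves nothing to compare after randomised treatment.

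**What to change.** 1. Reconcile Section 7.3.4, Appendix 1 and the lists in Sections 6.2.5 and 6.2.6 so that the PGIC is collected at Visit 6, before randomised medication is started, and at Visit 7. The timing of Visit 7 also differs (Week 14 in Section 6.2.6, Week 12 in Appendix 1) and must be reconciled.
2. In Section 9.1.2, name Visit 7 as the analysed visit. Compare arms with the Visit 6 PGIC as a covariate in an ordinal model or ANCOVA (preferred), or keep CMH as a row-mean-score test with a prespecified collapsed Visit 6 stratum.
3. Report the shift from Visit 6 to Visit 7 by arm.
4. State in Section 7.3.4 the period to which the rating refers.

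The cost is a few sentences. On the Appendix 1 schedule there is no added assessment; under Section 7.3.4 as written, a Visit 7 rating has to be added. The downside is small: a model replaces a simple test, and little is gained if the two ratings correlate weakly.
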